6. GENERAL ASPECTS OF THE STATISTICAL ANALYSIS

6.1. Key Definitions

The Study Day is the day relative to the date of treatment (Day 1). In other words,

$$\text{Study Day} = \text{Date} - \text{Date of treatment} + 1,$$

if Date is on or after Date of treatment; or

$$\text{Study Day} = \text{Date} - \text{Date of treatment},$$

if Date is before Date of dosing.

For efficacy endpoints, baseline values will be defined as the last value before ticagrelor is administered, which is expected to be on Day -2. The pre-treatment value is defined as the last value before study drug is administered, which is expected to be on Day 1 (up to 10 minutes prior to PB2452/placebo infusion). If Day 1 value is missing, the value prior to that will be used as pre-treatment.

For all other endpoints, unless otherwise specified, baseline is the last non-missing observation before exposure to study treatment PB2452 or placebo, which is expected to be the pre-study drug measurement on Day 1, or Screening if the Day 1 data are not available.

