4.1. Study Treatments and Dose Administration

This Phase 2B study is a randomized, double-blind, multicenter, placebo-controlled study conducted across United States. The study is designed to evaluate the efficacy of PB2452 in reversing the anti-platelet effects of ticagrelor and to evaluate the safety and tolerability of PB2452 in subjects aged 50-80 years old.

Approximately 200 subjects 50-80 years old inclusive will be enrolled across US or if needed other countries at 5-15 sites. The subjects will be randomized at a ratio of 3:1 receiving either the PB2452 investigational study drug or placebo. Hence, a total of approximately 150 subjects will be receiving PB2452 and approximately 50 subjects will be receiving placebo.

All subjects will be administered aspirin 81 mg daily for at least 7 days prior to initiation of ticagrelor pretreatment with a 180 mg oral loading dose of ticagrelor, followed by 90 mg bid for a total of 5 doses of ticagrelor. Two hours following the last dose of ticagrelor, subjects will be randomized to either PB2452 (investigational / study drug) or a matching placebo administered intravenously (IV) to assess reversal at peak ticagrelor plasma concentrations.

The infusion regimen is as follows:

- An initial IV bolus infusion consisting of a 6 g of study drug infused over 10 minutes followed immediately by an additional 6 g loading regimen of PB2452 infused over 4 hours,
- A maintenance regimen of 6 g infused over 12 hours will follow completion of the loading regimen for a total infusion time of approximately 16 hours.

No interim analysis or subsequent long-term extensions are planned.

Table 1 Schedule of Events

Procedure	Out patient		Out patient			Treatment (in house)			Out patient	Out patient
	Screening ^a		Check-in/ Pretreatment			Rand		Subject DC	FUP	FUP EOS
Study Day(s)	-45 to -4	-7	-3	-2	-1	1	2	3	7	35±3
Sign informed consent	X									
Inclusion/exclusion criteria	X		X		X					
Demographics	X									
Medical history	X									
Urine drug screen	X		X							
Urine alcohol screen	X		X							
Serum pregnancy test ^b	X		X							X
Serology testing	X									
Stool for occult blood	X									
Admission to study clinic			X							
Physical examination ^{c,d}	X ^c		X ^c						X ^d	X ^d
Vital sign measurements ^e	X		X			X	X	X	X	X
12-lead ECG ^f	X			X	X	X			X	X
Clinical laboratory testing	X		X		X		X		X	X
Randomization						X				
Drug administration										
ASA 81 mg QD ^g	X	X	X	X	X	X				
Ticagrelor administration ^h				X	X	X				

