- g ASA 81 mg will be taken on Days -7, -6, -5, -4, -3, -2, -1, and on Day 1 (2 hours before study drug is started). Subjects who enter the study already taking ASA daily must document a daily ASA 81 mg dose between Day -7 and Day -3. Patients will receive daily ASA 81 mg between Day -3 (or Day -2 if the patient took ASA 81mg on Day -3 prior to Check-in) and Day 1 at the clinical facility and will suspend further ASA dosing until discharge from the clinical facility.
- h Beginning in the morning on Day -2, a single dose of oral ticagrelor 180 mg will be given, followed by oral ticagrelor 90 mg every 12 hours for 4 additional doses through to Day 1 (2 hours before study drug is initiated; this will be 5 total doses of ticagrelor).
- i PB2452/placebo will be administered at Hour 0 of Day 1.
- j Blood samples for determination of plasma PB2452, plasma ticagrelor/TAM and unbound plasma ticagrelor/TAM will be collected within 10 minutes prior to the initiation of PB2452/placebo infusion (Hour 0) and at 5, 10, 30 minutes and 1, 2, 4, 8, 12, 20, 24, 36, and 48 hours after initiation of study drug infusion. And on days -2, 1, 2, 3, 7, and 35 ± 3 after initiation of study drug infusion.
- k Blood samples for PD analysis (PRU/VASP testing) will be collected at the following timepoints: Day -2 (up to 60 minutes prior to first ticagrelor dose) and Hour 0 (up to 10 minutes prior to PB2452/placebo infusion), 5, 10, 30 minutes, 1, 2, 4, 8, 12, 20, 24, 36 and 48 hours after initiation of PB2452/placebo infusion.
- If there is sufficient material leftover from PK and/or PD blood samples, additional platelet function-related biomarkers, such as P-selectin, will be tested to support hypothesis generation for future studies.
- l Subjects may be required to return to the site for collection of additional follow-up samples, if the sample collected at Day 35 ± 3 tests positive for treatment-emergent ADAs. These visits may occur approximately 3 months after the final study visit and approximately every 6 months thereafter or until antibody levels return to baseline level.
- m Infusion site assessments will be performed for all subjects within 15 minutes before initiation of PB2452/placebo infusion at Hour 0, 1, 3, 24, and 48 hours after initiation of PB2452/placebo infusion, and on Day 7.

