6.3. Missing Data

For subjects with missing data on efficacy endpoints, no imputation will be used. For binary endpoints, the missing data will be excluded from the calculation of proportions.

For the purpose of determining inclusion of AEs in the treatment-emergent AE (TEAE) summary tables, incomplete or missing AE onset and end dates will be imputed as follows:

Incomplete or missing onset dates (where UK and UNK indicate unknown or missing day and month, respectively):

- UK-MMM-YYYY: If the month and year are different from the month and year of the first dose of study drug, assume 01-MMM-YYYY. If the month and year are the same as the first dose of study drug month and year, and the end date (after any imputation) is on or after the dose of study drug, then assume the date of the dose of study drug. If the month and year are the same as the dose of study drug month and year and the end date (after any imputation) is prior to the dose of study drug, then assume the end date for the onset date.
- DD-UNK-YYYY or UK-UNK-YYYY: If the year is different from the year of dose of study drug, assume DD-JAN-YYYY or 01-JAN-YYYY of the onset year, respectively. If

the year is the same as the dose of study drug year, and the end date (after any imputation) is on or after the dose of study drug, then assume the date of the dose of study drug for the onset date. If the year is the same as the dose of study drug, and the end date (after any imputation) is prior to the dose of study drug, then assume the end date for the onset date.

- Missing onset date: If the onset date is completely missing and the end date (after any imputation) is on or after the start of administration of study drug, then assume the onset date to be the start of administration of study drug. If the end date (after any imputation) is prior to the start of administration of study drug, then assume the end date to be the onset date.

Incomplete or missing end dates (where UK and UNK indicate unknown or missing day and month respectively):

- UK-MMM-YYYY: Assume the last day of the month;
- DD-UNK-YYYY or UK-UNK-YYYY: Assume DD-DEC-YYYY or 31-DEC-YYYY, respectively;
- Missing end date: Assume 31-DEC-YYYY, where YYYY is the year of the start of administration of study drug.

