An AE with missing onset time but with an onset date the same as the start of administration date of study drug will be classified as treatment-emergent, unless the AE was reported pre-dose with the same or worse intensity or frequency.

Medications with missing start time but with a start date the same as the start of administration of study drug date will be considered as being taken on or after the initiation of study drug, unless the electronic case report form (eCRF) question “Was the medication/therapy taken prior to the study” is answered as “Yes” which is considered as being taken prior to the initiation of study drug.

Handling of missing PK data is specified in Section 9.5 and handling of PD data is specified in Section 9.6.

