The dichotomous secondary endpoints will be compared between the treatment groups using Fisher's Exact test at two-sided 5% significance level.

9.3. Other Efficacy Endpoints:

The following PD parameters may be calculated and summarized using %baseline/actual PRU data from the VerifyNow assay. The maximal endpoints will be presented as other continuous endpoints using summary statistics. The median time-to-event endpoints will be summarized using the Kaplan Meier method. Time will be censored if the event is not attained before the study end.

APRUMax	Maximal actual PRU
APRUMax4h	Maximal actual PRU within 4 h
PRUmax	Maximal percent of baseline PRU
TPRUMax	Time to maximal actual PRU
TPRU180	Time to 180 or higher actual PRU, calculated as the first observed time point (no extrapolation) when the actual PRU reaches 180 or above
TPRU200	Time to 200 or higher actual PRU, calculated as the first observed time point (no extrapolation) when the actual PRU reaches 200 or above

TPRU220	Time to 220 or higher actual PRU, calculated as the first observed time point (no extrapolation) when the actual PRU reaches 220 or above
TPRU60%	Time to 60% of baseline PRU, calculated as the first observed time point (no extrapolation) when %baseline PRU reaches 60% or above
TPRU80%	Time to 80% of baseline PRU, calculated as the first observed time point (no extrapolation) when %baseline PRU reaches 80% or above
TPRU100%	Time to 100% of baseline PRU, calculated as the first observed time point (no extrapolation) when %baseline PRU reaches 100%

Similar parameters may also be reported for PRI.

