13. ANALYSIS CONVENTIONS

Post-text tables and listings will be prepared in accordance with the current ICH Guidelines. The information and explanatory notes to be provided in the “footer” or bottom of each table and listing will include the following information:

1. Date and time of output generation;
2. SAS® program name that generates the output;
3. Any other output specific details that require further elaboration.

In general, tables will be formatted with a column displaying findings for all subjects combined. Row entries in tables are made only if data exists for at least one subject (i.e., a row with all zeros will not appear). The only exception to this rule applies to tables that list the termination status of subjects (e.g., reasons for not completing the study). In this case, zeros will appear for study termination reasons that no subject satisfied. The summary tables clearly indicate the number of subjects to which the data apply and unknown or not performed are distinguished from missing data.

This section details general conventions to be used for the statistical analyses. The following conventions will be applied to all data presentations and analyses.

- All summary tables will include the analysis set sample size (i.e., number of subjects).
- Study Day 1 is defined as the first day the subject is exposed to the study drug. All *study days* are determined relative to the day of exposure to the study drug
- Baseline values will be defined as those values recorded closest to, but prior to, the first study treatment on Day 1 for all measurements except for PD/efficacy endpoints. For these endpoints baseline is the last value before ticagrelor is administered.
- Change from baseline will be calculated as follows:

$$\text{Change} = \text{Post-baseline value} - \text{baseline value}.$$

- Subject data obtained during unscheduled visits/assessments will not be summarized but will be included in subject data listings only; except for the determination of minimum % inhibition of PRU or PRI within 4 hours post-baseline. Unscheduled visit values will not be used to impute missing scheduled visit values, except for baseline calculation.
- No visit windows will be used to select efficacy data for analysis. Data collected at the nominal visit will be used for analysis (note that Day 35 is defined as 35 \pm 3, but will be reported as Day 35/End-of-study for simplification).

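### Does the SAP's fallback for a missing Hour 0 platelet reading damage the percent-reversal endpoints?

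*SAP*

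**What the plan says.** For efficacy endpoints, SAP 6.1 states that "baseline values will be defined as the last value before ticagrelor is administered, which is expected to be on Day -2". It defines the pre-treatment value as the last reading before study drug, expected on Day 1 shortly before the infusion, and adds: "If Day 1 value is missing, the value prior to that will be used as pre-treatment".

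Footnote k to SAP Table 1 (section 4.1) lists the platelet-function samples due before study drug: "Day -2 (up to 60 minutes prior to first ticagrelor dose) and Hour 0 (up to 10 minutes prior to PB2452/placebo infusion"). The table shows none on Day -1.

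SAP 3.2 and 9.2 define percent reversal as the rise from the pre-treatment reading divided by baseline minus pre-treatment. Percent reversal of PRU and of PRI stand second and third in the ordered list of continuous secondary endpoints in SAP 9.2.

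Three other passages bear on missing readings:

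- SAP 6.3: "For subjects with missing data on efficacy endpoints, no imputation will be used".
- SAP 6.3 again: "Handling of missing PK data is specified in Section 9.5 and handling of PD data is specified in Section 9.6". The last subsection of Section 9 is "9.3. Other Efficacy Endpoints", so the second reference leads nowhere.
- SAP 13: "Unscheduled visit values will not be used to impute missing scheduled visit values, except for baseline calculation".

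Footnote q of the protocol's schedule differs from SAP footnote k. It names Day 1 beside Day -2 for the sample before the first ticagrelor dose, although that dose is given on Day -2. The Day 1 procedure list in Protocol 6.1 has only one platelet sample before the infusion, at Hour 0.

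**The concern.** The pre-treatment value is meant to show how far ticagrelor has suppressed the platelets just before reversal starts. Study drug is given two hours after the last ticagrelor dose "to assess reversal at peak ticagrelor plasma concentrations". With Hour 0 missing, the only earlier reading on the SAP's schedule is the uninhibited one from Day -2. The fallback would then label a normal reading as the suppressed level and subtract the baseline from itself in the denominator.

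The surrounding text does not clearly help. SAP 6.3 rules out imputation, the pointer for PD data is dead, and SAP 13 appears to bar an unscheduled redraw from standing in. If wrong numbers entered the comparison, two endpoints near the top of the secondary testing order would be affected.

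**Working it through.** The plan states no figure on this point, so the check applies the rule as written.

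**Inputs.** Baseline B is the Day -2 reading (SAP 6.1). Pre-treatment P is the Hour 0 reading or its fallback (SAP 6.1). T is a post-dose reading. Percent reversal is R = 100 × (T − P) / (B − P) (SAP 3.2 and 9.2). The PRU levels below are assumed, for illustration only.

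**1. Hour 0 present.** With B = 220, P = 20 and T = 210, R = 100 × (210 − 20) / (220 − 20) = 100 × 190/200 = 95%.

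**2. Hour 0 missing, SAP schedule.** The fallback gives P = B = 220, so B − P = 0. For T = 30, 210 and 220 the quotients are −190/0, −10/0 and 0/0. None has a value. This does not depend on the assumed levels, because the fallback makes P equal to B for any subject. The same holds for PRI.

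**3. Hour 0 missing, no fallback.** P is missing, so R is missing.

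**4. Comparison.** Steps 2 and 3 put the same set of subjects into the two t-tests. On scheduled samples the difference is 0 subjects.

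**5. Other endpoints.** The primary endpoint is 100 × (B − T) / B. With B = 220 and T = 210 it is 100 × 10/220 = 4.5%, whether or not Hour 0 was measured. Minimum percent inhibition of PRI has the same form. The 4-hour AUCs, the proportion reaching PRU 180 and the response-rate proportions do not contain P.

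**6. If protocol footnote q means an extra Day 1 sample before the morning ticagrelor dose.** The fallback would then pick an on-ticagrelor reading. With that reading assumed to be 40, R = 100 × (210 − 40) / (220 − 40) = 170/180 = 94.4%. On this reading the rule works.

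**7. How many subjects reach the rule.** The documents give no missing rate. At an assumed 1% to 5%, that is 200 × 0.01 = 2 to 200 × 0.05 = 10 subjects.

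**The case for a change.** The best argument for a change is that a written derivation should not be harmless only because a division fails. There are three strands to it.

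*A clearer rule could recover subjects through an unscheduled redraw.* SAP 6.1 may already allow this. Its fallback starts only when the Day 1 value is missing. A redraw between the final ticagrelor dose and study drug is a Day 1 value and is the last one before study drug. SAP 13 leaves some tension with that reading, but neither document schedules a redraw, so no recovery can be counted. A rule admitting only readings after the final ticagrelor dose could also lose subjects, because it would reject the footnote q sample in step 6.

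*SAP 6.1 and 6.3 contradict each other.* They can be read together. SAP 6.3 is the general statement about missing endpoints, and 6.1 is a specific rule about which observed reading enters a derivation.

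*The rule can produce a number, and a bad one.* SAP 13 admits unscheduled values for baseline only. Suppose a scheduled Day -2 reading of 218, an unscheduled pre-ticagrelor repeat of 222, no Hour 0 reading, and a placebo subject reaching 60. If 222 is the baseline and 218 the fallback, R = 100 × (60 − 218) / (222 − 218) = −3950%. That value alone would add −3950/50 = −79 points to the mean of 50 placebo subjects. The arithmetic is right. The case needs an unplanned Day -2 repeat and a missing Hour 0 sample in the same subject, together with a reading of the SAP that accepts the repeat for baseline but rejects it as the last value before study drug. A percentage of that size would also stand out in any listing.

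What stands is that the sentence in 6.1 is loosely written, the Section 9.6 reference is a clerical slip, and SAP footnote k and protocol footnote q do not match. None of these is shown to alter a result.

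**Conclusion.** The reading of the text is right: on the SAP's own schedule the fallback returns the baseline, and percent reversal is undefined for that subject. No change follows, because there is nothing to gain. The subject is missing for percent reversal of PRU and PRI with or without the sentence, 0 subjects differ on scheduled samples, and no test is shown to change. The defect is visible when it occurs: the calculation has no answer, and an analyst would set the value to missing, in line with SAP 6.3.

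This rests on SAP footnote k being the operative schedule. If protocol footnote q does describe a second Day 1 sample, the fallback selects an on-ticagrelor reading and gives a defined result. It also sets aside the unscheduled Day -2 repeat described above, which neither document plans. The 2 to 10 subjects who might reach the rule depend on an assumed missing rate of 1% to 5%. That range counts subjects without an Hour 0 value, not subjects whose result would change.

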Administration PB2452 or placebo ⁱ						X				
PK sampling ^j :										
Plasma PB2452										
Plasma Ticagrelor/TAM				X		X	X	X	X	X
Unbound Plasma ticagrelor/TAM										
PK urine sampling				X		X	X	X		
PD sampling (PRU/VASP) ^k				X		X	X	X		
Biomarkers					X		X		X	X
Serum immunogenicity			X			X			X	X ^l
Infusions site assessment ^m						X	X	X	X	X
Adverse events	X	X	X	X	X	X	X	X	X	X
Concomitant Medications ⁿ	X	X	X	X	X	X	X	X	X	X
Discharge from clinic ^o								X		

Abbreviations: ADA=anti-drug antibody; ASA= aspirin; BMI=body mass index; DBP=diastolic blood pressure; DC = discharged; ECG=electrocardiogram; EOS=end of study; FUP=follow-up; HR=heart rate; PD=pharmacodynamics; PK=pharmacokinetics; PRU=P2Y₁₂ reaction units; QD=once daily; Rand=Randomization; RR=respiratory rate; SBP=systolic blood pressure; TAM=ticagrelor active metabolite AR-C124910XX; VASP=vasodilator-stimulated phosphoprotein.

- a Screening Period = Days -45 to -4 (including Day -7, when ASA is started).
- b Serum pregnancy test for women of childbearing potential only.
- c A full physical examination is conducted at Screening, Day -3 and Day 35 ± 3 . Height and BMI calculation are completed at Screening and Day 35 ± 3 only. Weight is collected at Screening, Day -3 and Day 35 ± 3 .
- d Brief physical examination and querying the subject concerning any changes from baseline.
- e Vital sign measurements (SBP and DBP, oral body temp, RR, and HR) will be collected at screening, check-in, before dosing (30 to 60 minutes prior to the initiation of the study drug infusion) and at 15, 30, 45, 60 min, 24 and 48 hours following initiation of study drug. Vital Signs are also collected on Day 7 and 35 ± 3 . Vital signs at 15, 30, 45, and 60 minutes following infusion require only SBP and DBP, and HR.
- f 12-lead ECGs will be obtained at Screening before initiation of PB2452/placebo, pre-treatment Day -1, and on treatment Days 1, 2, 7 and 35 ± 3 . The specific time points for 12-lead ECG on Day 1 and 2 will be pre-dose, after bolus, end of infusion, and after 24 hours from initiation of infusion. ECGs will be collected anytime on Day 3, 7, and 35 ± 3 .

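### Does the Day 1 or Screening wording in SAP 6.1 leave the laboratory baseline undefined?

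*SAP*

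**What the plan says.** For every endpoint outside efficacy, unless stated otherwise, SAP 6.1 gives the rule "baseline is the last non-missing observation before exposure to study treatment PB2452 or placebo". A descriptive phrase follows: "which is expected to be the pre-study drug measurement on Day 1, or Screening if the Day 1 data are not available".

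SAP 13 repeats the rule. Baseline is "those values recorded closest to, but prior to, the first study treatment on Day 1 for all measurements except for PD/efficacy endpoints", and that section is introduced with "The following conventions will be applied to all data presentations and analyses". It names no Screening fallback. It also lets unscheduled values count when baseline is derived.

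In SAP Table 1 (section 4.1) the row "Clinical laboratory testing" is marked at Screening and Days -3, -1, 2, 7 and 35. The protocol's schedule (1.1 and Appendix 3) marks the same visits. Neither marks Day 1. The protocol's Day 1 procedure list (6.1) only has the Day -1 results reviewed before randomization.

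The laboratory baseline is used in SAP 10.2, which tabulates actual values and changes by arm and visit with descriptive statistics.

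Protocol Version 2 (footnote i of the schedule; sections 6.1 and 6.1.1.7) sends all scheduled laboratory tests to the central laboratory except Day -1, which is local so that results are available before randomization. The SAP does not mention local results.

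**The concern.** Two things look wrong.

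First, the descriptive phrase cannot hold for laboratory data. With no Day 1 sample scheduled, the expected case never occurs, and a literal reader would fall back to Screening for every subject. That passes over two of the three scheduled pre-dose samples, Days -3 and -1. The rule and the phrase attached to it then point to different visits, and two programmers could produce different change-from-baseline tables.

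Second, if the rule is followed and Day -1 is taken, Version 2 sets a local baseline against central values at Days 2, 7 and 35. A systematic difference between laboratories would appear as a change after dosing, and the SAP does not say whether local values may serve as baseline. Laboratory safety is part of a secondary endpoint, so a spurious within-arm shift could mislead someone reading the tables.

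**Working it through.** No figure in the plan is at stake, so the check applies each reading to the schedule.

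**Step 1. Pre-dose visits and what each reading selects.** Visits are from SAP Table 1. Screening covers Days -45 to -4.

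| Data | Scheduled pre-dose visits | Last pre-dose value (the rule) | Day 1, else Screening (the phrase) |
|---|---|---|---|
| Vital signs | Screening, -3, 1 | Day 1 | Day 1 |
| ECG | Screening, -1, 1 (the SAP table also marks -2) | Day 1 | Day 1 |
| Anti-drug antibodies | -3, 1 | Day 1 | Day 1 |
| Laboratory | Screening, -3, -1 | Day -1 | Screening |

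The Day 1 values for the first two rows are confirmed by the table's footnotes: vital signs are taken "before dosing (30 to 60 minutes prior to the initiation of the study drug infusion", and for ECG, "The specific time points for 12-lead ECG on Day 1 and 2 will be pre-dose, after bolus, end of infusion". The antibody sample on Day 1 must precede the infusion (protocol schedule, footnote s). Among these four data types the phrase fails only for laboratory data.

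**Step 2. Size of the visit difference.** Under the study-day formula in SAP 6.1 there is no Day 0, so Day -n is n days before dosing.
- Screening against Day -1: 4 - 1 = 3 to 45 - 1 = 44 days older.
- Screening against Day -3: 4 - 3 = 1 to 45 - 3 = 42 days older.

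**Step 3. Is the baseline defined?** The rule gives one answer in each case:
- Day -1 as scheduled.
- A later unscheduled pre-dose value, if one exists (SAP 13 allows it).
- Day -3, if local Day -1 results are not in the analysis dataset.
- Screening for TSH, which is tested only then. The phrase agrees here, and no later scheduled value exists to compare.

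None of these requires the Screening fallback for an analyte that has a later pre-dose result.

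**Step 4. Effect of a local baseline.** Write the local reading as the central reading plus an offset d. Then

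observed change = central follow-up - (central baseline + d) = true change - d.

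The mean change in each arm moves by minus the mean of d. Allocation is random and both arms follow the same rule, so the expected d is the same in both. The difference in expected change is (PB2452 change - d) - (placebo change - d) = PB2452 change - placebo change. Chance imbalance of sites between arms would add noise but no bias. The actual values at Days 2, 7 and 35 do not contain d. The documents give no value for d, so its size cannot be computed.

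**Step 5. The alternative baseline.** Day -3 is the last scheduled central sample before study drug. Ticagrelor starts on Day -2 (SAP Table 1, footnote h). A Day -3 baseline removes d but places any ticagrelor effect on laboratory values inside the within-arm change. A Day -1 baseline is taken after ticagrelor has started.

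**The case for a change.** The best argument for a change is that it costs almost nothing. A sentence whose explanation disagrees with its rule invites divergent programming. SAP 6.1 shows elsewhere that a cleaner fallback was available: for the pre-treatment efficacy value it simply steps back to the previous measurement. The local and central gap arises under the rule itself, so pointing to the rule does not close it. Repeat tests may also be local or central at the investigator's discretion (protocol 6.1.1.7).

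Part of this stands. The phrase is inaccurate for laboratory data, and the SAP has no stated policy on local values.

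The rest is weaker. The phrase is introduced as an expectation, and SAP 13 restates the rule for all analyses without it, so a programmer who reads both sections takes the last pre-dose record. Deleting the phrase would not alter any table built that way. The mixing of laboratories is shown only for visits under Version 2, dated 28 May 2021. SAP section 2 refers to the protocol of 12 August 2019, which is not available, and the SAP's own schedule has no local-laboratory footnote. Mixing also requires that local Day -1 results reach the analysis dataset, which no section states for these values. If they do not, the rule already yields Day -3. Finally, a Day -3 central baseline is a choice between two imperfections, and correcting the visit mismatch does not require it.

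**Conclusion.** The observation about the schedule is correct, but it does not call for a change. The Screening wording is a generic description that fits vital signs, ECG and antibody data and misses laboratory data. The operative rule, stated twice, still gives a defined laboratory baseline: Day -1 as scheduled. This rests on reading the phrase as description, which its wording and SAP 13 both support.

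The silence on local values is a gap that analysts ordinarily fill when they specify the datasets, by flagging the source laboratory and noting it under the table. Its consequence is confined to descriptive within-arm changes in SAP 10.2, and only for subjects whose Day -1 test was local and was entered in the dataset. The documents give neither the number of such subjects nor the size of any offset. No hypothesis test uses this baseline, and SAP 10.2 plans no between-arm laboratory difference. The placebo arm would be expected to show the same artefact and so reveal it. Under protocol 6.1.1.7, the clinical significance of a laboratory change is judged against the Screening value, not this baseline. Choosing between Day -1 (local under Version 2, on ticagrelor) and Day -3 (central, before ticagrelor) is a fair trade-off, and the existing rule is a reasonable side of it.
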